6.6.2 Primary Safety Endpoint

The co-primary analysis of safety will test if the mean change in fellow eye visual acuity of the therapeutic group from baseline to 12 weeks is non-inferior to the mean change in fellow eye visual acuity of control group within a margin of 0.10 logMAR. The formal hypothesis being tested are:

$$H_0: \mu_{\text{therapeutic}} - \mu_{\text{control}} \geq \delta$$

Statistical Analysis Plan		Page 18 of 23
Sponsor Luminopia	Study Luminopia One Amblyopia Vision Improvement Study	

$$H_a: \mu_{\text{therapeutic}} - \mu_{\text{control}} < \delta$$

where μ is the change from baseline (follow-up - baseline) for both the control and therapeutic participants and δ is the non-inferiority window of 0.10 logMAR. The statistical test is a two-sample one-sided T-test which will be done at the 0.05 level of significance. An upper 95% confidence limit for the difference will also be presented. The endpoint will be considered met if the p-value is < 0.05 .

The endpoint will be evaluated using the ITT population with no imputation for missing data. Assessments from out of window visits will be considered missing in the primary analysis. Supplementary analysis will be provided based on ITT with imputation, PP and AT cohorts, as described in the primary efficacy endpoint analysis.

In addition to the formal test on the mean change in fellow eye visual acuity, the primary safety endpoint will report the frequency and severity of all related Adverse Events (anticipated and unanticipated). Count of events, percent of participants who experienced an event, and an exact 95% confidence interval of the event rates will be presented for each treatment group by event type. No formal hypothesis testing will be performed. Event rates will be summarized for clinical interpretation. Safety analyses on Adverse Events will be based on the AT analysis cohort.

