6.2 Analysis Populations

The following analysis populations are defined for analysis:

- 1. Intention-to-treat (ITT) Analysis Set:** The intention-to-treat (ITT) population consists of all enrolled participants who were subsequently randomized. The ITT set will be analyzed according to randomized treatment assignment regardless of treatment actually received. The ITT population will not include participants who did not meet eligibility criteria at the time of enrollment and are ultimately deemed ineligible for the study, including participants who are withdrawn from the study due to insufficient internet.
- 2. As-Treated Analysis Set:** The as-treated (AT) population consists of participants enrolled and randomized, however treatment group assignment for the purposes of analysis will be based on the actual treatment received. Participants randomized to the Luminopia One group with ≤ 25% adherence in device use at 12 weeks will be analyzed as control participants.
- 3. Per-Protocol Analysis Set:** The per-protocol (PP) population consists of all ITT participants who were treated according to randomized assignment, who had adherence > 25% in Luminopia One Use for the therapeutic group, and who had no major protocol deviations that could affect the endpoints of interest. Protocol deviations will be reviewed and defined as major prior to analysis

Statistical Analysis Plan		Page 15 of 23
Sponsor Luminopia	Study Luminopia One Amblyopia Vision Improvement Study	

of study outcomes. The 25% adherence threshold for the PP population was determined from pilot trials on Luminopia One, in which all enrolled participants with > 25% adherence and no major protocol deviations showed improvements from using the therapeutic. Adherence will be captured while maintaining masking of the study in accordance with the Masking Plan.

The ITT population will be used for analysis and interpretation of the primary and secondary efficacy endpoints and the co-primary safety endpoint assessing BCVA in the fellow eye. Supportive analysis for the primary and secondary efficacy endpoints will be performed using the PP population to provide insight into the potential impact of protocol deviations on the primary results of the study. The AT cohort will be used to characterize and assess safety, including the co-primary safety endpoint evaluating frequency and severity of all related Adverse Events, as well as supportive efficacy analyses.

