6.6.3 Study Success

The study will be considered a success if both the primary efficacy and primary safety endpoints are passed. The 12-week visit measurements in the therapeutic and control groups will determine success and failure of the trial for both primary safety and efficacy endpoints. Measurements from the 24-week visit, for participants in the control group who switch over to the therapeutic after the 12-week visit will not be part of the primary analysis and will not define study success.

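### The fellow-eye noninferiority test is decided on ITT alone; low device use favours passing, and the planned PP and AT analyses carry no weight in the decision

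*SAP*

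**What the plan says.** SAP 6.6.2 tests whether the therapeutic-minus-control difference in mean fellow-eye change is below +0.10 logMAR, using a one-sided two-sample t-test at 0.05. On the deciding set it states: "The endpoint will be evaluated using the ITT population with no imputation for missing data". Out-of-window visits count as missing.

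Section 6.2 agrees on the deciding set: "The ITT population will be used for analysis and interpretation of the primary and secondary efficacy endpoints and the co-primary safety endpoint". It defines that set as follows: "The ITT set will be analyzed according to randomized treatment assignment regardless of treatment actually received".

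The other sets appear in 6.6.2 only as follows: "Supplementary analysis will be provided based on ITT with imputation, PP and AT cohorts". Section 6.2 is narrower on PP: "Supportive analysis for the primary and secondary efficacy endpoints will be performed using the PP population". It does not name PP for the fellow-eye endpoint, so the two sections do not match.

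PP requires adherence above 25% in the therapeutic arm. For AT, 6.2 says: "Participants randomized to the Luminopia One group with ≤ 25% adherence in device use at 12 weeks will be analyzed as control participants".

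The success rule in 6.6.3 is: "The study will be considered a success if both the primary efficacy and primary safety endpoints are passed". No condition on PP or AT enters it, and no rule covers a PP or AT result that disagrees with ITT.

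**The concern.** The SAP uses the same deciding set for a superiority test (amblyopic eye) and a noninferiority test (fellow eye). Low use acts in opposite directions on the two. In the superiority test, children assigned to the device who hardly use it shrink a real benefit and make success harder. In the noninferiority test they shrink a real harm, move the difference away from +0.10 and make success easier.

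The SAP draws a line at 25% adherence. A device-arm child at or below it is left out of PP and counted as a control in AT. In the one analysis that decides the safety endpoint, the same child counts fully as a device-arm child.

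At stake is a co-primary safety conclusion about the fellow eye in children aged 4 to 7. If the device harmed that eye in those who use it, the endpoint could still be met on ITT. A contrary PP or AT result would then have no defined consequence.

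**Working it through.** **Inputs from SAP section 5:** fellow-eye SD 0.10; margin +0.10; expected changes -0.05 and -0.02, so a difference of -0.03; 66 per arm; one-sided alpha 0.05 (z = 1.645); power 90% (z = 1.282).

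**Assumptions, not in the SAP:** q, the share of low users among device-arm children with an in-window 12-week visit, is varied from 0% to 30%. Harm is +0.10 in users; in low users it is zero, then half. A single look and a normal approximation are used for the pass probabilities.

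**1. The plan's own figure.** Section 5 says the safety test needs fewer than 132 participants.
- n per arm = 2 × 0.10² × (1.645 + 1.282)² / (0.10 − d)².
- At d = -0.03: 10.1, so 11 per arm (22 in total).
- At d = 0: 17.1, so 18 per arm (36 in total).
- The statement is confirmed, with a wide reserve of power. The efficacy-driven 132 also reproduces: the two-look design gives 131.0, or 132 in equal arms.

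**2. ITT passing threshold without dilution.** SE = 0.10 × √(2/66) = 0.0174. The test passes if the observed difference is below 0.10 − 1.645 × 0.0174 = 0.071.

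**3. ITT with low users unharmed.**
- Difference d = 0.10 × (1 − q).
- Device-arm variance = 0.10² + q(1 − q) × 0.10²; the second term arises because the arm is a mixture.
- SE = √[(device-arm variance + 0.10²)/66].
- P(pass) = Φ[(0.10 − d)/SE − 1.645].

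| q | d | SE | P(pass) |
|---|---|---|---|
| 0% | 0.100 | 0.0174 | 5% |
| 10% | 0.090 | 0.0178 | 14% |
| 20% | 0.080 | 0.0181 | 30% (29.5%) |
| 25% | 0.075 | 0.0182 | 39% |
| 30% | 0.070 | 0.0183 | 50% |

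**4. ITT with low users at half the harm (+0.05).** Now d = 0.10 × (1 − q) + 0.05q, and the mixture term is q(1 − q) × 0.05².
- q = 20%: d = 0.090, SE = 0.0176, P(pass) about 14%.
- q = 30%: d = 0.085, SE = 0.0176, P(pass) about 21%.

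**5. PP under the same harm.** Only users remain, so d = 0.10 and P(pass) = Φ(−1.645) = 5% at any q, provided adherence is unrelated to harm.

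**6. AT under the same harm.** Low users move to control. If they are unharmed, the difference is again 0.10 and P(pass) = 5%. If they carry half the harm, the control mean rises and AT passes about 12% of the time at q = 20% and 15% at q = 30%.

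**7. Power of the PP test when the device is acceptable**, with 40% of the device arm excluded (about 40 against 66):
- true difference -0.03 or 0: at least 99.9%;
- +0.02: about 99%;
- +0.03: about 97%.

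**The case against.** Several points on the other side stand.

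- **No stated error rate is broken.** A reader might infer that the 5% level fails. It does not: 6.6.2 states its hypotheses on the means of the two groups, and ITT tests that as-randomized contrast at 5%. Section 5 does describe the safety question in terms of use of the device, but that wording defines no separate target among users, and the SAP says nothing about labelling. What rises is the chance of passing when harm among users reaches the margin.
- **Not every child who stops dilutes the difference.** A child without an in-window 12-week visit is dropped as missing. Children withdrawn for insufficient internet are outside the set the SAP calls ITT. Only low users who attend in window have this effect.
- **AT is not useless.** It might seem that placing low users in control defeats it. If low users are unharmed, AT restores the 5% level; if they are partly harmed, it does so only in part. It is a reasonable supportive analysis.
- **The analyses are already promised.** A harm confined to users would appear beside the ITT result. The gap is that it would change nothing.
- **The size is conditional.** A 25% cut-off does not show that the sponsor expects many low users. The SAP plans for a small fellow-eye benefit (-0.03), where dilution does not help the test.
- **PP is imperfect.** It filters one arm after randomization. If children whose fellow eye worsens stop using the device, PP removes the harmed children. It therefore cannot replace ITT, but a rule requiring both can never be easier to pass than ITT alone.

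**Conclusion.** The point holds as a weakness in the decision rule. The fellow-eye endpoint is decided on the set in which low use favours passing, and the planned checks have no influence on the outcome. With harm at the margin in users and none in low users, the chance of passing rises from 5% to 14%, 30% and 50% at 10%, 20% and 30% low users. With half the harm in low users it is about 14% at 20% and 21% at 30%.

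These figures rest on an assumed low-user share, SD 0.10, 66 per arm with 12-week data, and a single look. The 5% for PP also needs adherence to be unrelated to harm. The figures show how the rule behaves if there is harm; they are no evidence that there is any. The change is worth making because it is cheap and can only tighten the safety conclusion.

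**What to change.** - In 6.6.2 and 6.6.3, declare the fellow-eye endpoint met only if the one-sided test against +0.10 logMAR passes in both the ITT and the PP set.
- Keep ITT as the randomized comparison and for the efficacy endpoint. Report AT alongside as supportive.
- Reconcile 6.2, which names PP for efficacy endpoints only, with 6.6.2, which promises PP for the fellow-eye endpoint.

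The cost is a few sentences and no new analysis. The success rule becomes slightly harder. The loss of power is negligible at the expected difference of -0.03 and still small at +0.02 or +0.03, even with 40% of the device arm excluded.

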6.6.3 Study Success

The study will be considered a success if both the primary efficacy and primary safety endpoints are passed. The 12-week visit measurements in the therapeutic and control groups will determine success and failure of the trial for both primary safety and efficacy endpoints. Measurements from the 24-week visit, for participants in the control group who switch over to the therapeutic after the 12-week visit will not be part of the primary analysis and will not define study success.

6.6.4 Secondary Efficacy Endpoints

No formal hypothesis testing will be performed for the secondary endpoints; any statistical comparisons made will be considered exploratory and no adjustments for multiple testing will be made.

The secondary endpoints will be evaluated using the ITT population with no imputation for missing data. Supplementary analysis may be provided based on the PP and AT cohorts. Sensitivity analyses, including missing data imputation, may be performed if necessary. Unless otherwise stated, only in-window follow-up visits will be included in the endpoint analyses.

6.6.4.1 VA at 12 Weeks of 2.0 or more lines

The proportion of participants with amblyopic-eye BCVA improvement of ≥ 2 lines of VA (≤ -0.2 logMAR) at 12 weeks (Visit 4) from baseline will be presented by group and an exact 95% confidence interval will

Statistical Analysis Plan		Page 19 of 23
Sponsor Luminopia	Study Luminopia One Amblyopia Vision Improvement Study	

also be provided. Subjects with available data at baseline and an in-window 12-week visit will be included in the analysis.

6.6.4.2 Stereoacuity at 4, 8, and 12 Weeks

A secondary analysis will report the mean change in stereoacuity in each treatment group from baseline to 4, 8 and 12 weeks along with 95% confidence intervals about the mean change. Subjects with available data at baseline and an in-window follow-up visit will be included in the analysis.

Stereoacuity is evaluated with the Titmus Fly and Randot Preschool tests. The final stereoacuity measurement used for analysis for each visit is the lower, i.e. better, score between the two tests. The log transformation of the final score is used for analysis and back-transformed for displaying summary results.

6.6.4.3 VA at 4 and 8 Weeks

The primary endpoint analysis will be repeated for mean change in amblyopic eye BCVA from baseline to 4 and 8 weeks of treatment with Luminopia One will be compared to continued refractive correction. Mean change and 95% confidence intervals will be presented. Sensitivity and supplementary analyses may be performed as needed. Subjects with available data at baseline and an in-window follow-up visit will be included in the analysis.

6.6.4.4 Adherence at 4, 8, and 12 Weeks in the Luminopia One Group

A secondary analysis will report the mean adherence from baseline to 4, 8, and 12 weeks along with 95% confidence intervals about the mean adherence in refractive correction wear, and at 12 weeks in Luminopia One use.

6.6.5 Secondary Safety Endpoints

Safety analyses will be performed on the AT population. Results from any hypothesis testing will be considered exploratory and no adjustments for multiple testing will be made.

6.6.5.1 Adverse Events

AEs will be tabulated with the number of events and participants with event for each event type as described in the primary safety analysis. Additional summaries may be provided as necessary. Rates will be reported as the number of participants who experience at least one event during the analysis interval out of the total number of participants.

6.7 Subpopulation and Exploratory Analyses

The mean change in amblyopic eye BCVA from baseline to 12 weeks will be evaluated in subpopulations based on baseline factors in exploratory analyses and used to suggest hypotheses for further

Statistical Analysis Plan		Page 20 of 23
Sponsor Luminopia	Study Luminopia One Amblyopia Vision Improvement Study	

investigation in future studies. The following baseline factors are of interest: prior amblyopia treatment vs no prior amblyopia treatment, type of amblyopia (amblyopia without vs with strabismus), age (≤ 5 vs > 5), and baseline VA where the range of baseline VA is split into two groups (better than 20/100 vs 20/100 or worse). The general approach for these exploratory analyses will be to conduct an analysis similar to the primary analysis adding an interaction for treatment and the subgroup covariate of interest. If the p-value for the interaction term is < 0.15 , additional exploratory analysis may be performed to understand any variations in the outcomes by subgroup.

Additional subgroups may be defined during the analysis phase for investigative purposes. Exploratory analyses will also evaluate the relationship between adherence and mean change in amblyopic eye VA at the primary endpoint visit in the therapeutic group and will evaluate the change in amblyopic-eye VA from the 12-week visit to the 24-week visit for participants who were initially randomized to the control group and switched over to the therapeutic at the 12-week visit.

6.8 Site Poolability Analyses

Data from this trial will be pooled across study site for the purposes of analysis. To demonstrate poolability of the primary endpoint data, the change in amblyopic eye BCVA between baseline and 12 weeks will be calculated for each participant. This value will be used as the dependent variable in a linear model. The independent predictors will be study site, treatment group, and a study site by treatment group interaction. If the interaction term is considered non-significant then the data will be pooled across site for the purposes of analysis. If the interaction term is considered significant then the analysis of the primary endpoint will have to be adjusted for study site. A significance level of 0.15 will be used for this analysis. Sites with fewer than 5 participants enrolled may be combined into one site for purposes of this analysis.

6.9 Interim Analyses

Statistical Analysis Plan		Page 21 of 23
Sponsor Luminopia	Study Luminopia One Amblyopia Vision Improvement Study	

6.9.2 Group Sequential Design

A group sequential design will be employed to allow for early stopping due to either success (rejecting the null hypothesis) or futility. The goal of the group sequential design is to conserve precious time and resources and prevent unnecessary enrollment of participants if there is no observed difference in effect between groups or if there is a significant effect in favor of Luminopia One. It is important to allow for early stopping for success since there is a real possibility the therapeutic could perform significantly better than expected.

Boundaries for both alpha and beta will be calculated using a power cumulative error spending function. The mathematical form of this spending function is:

$$E(t, \rho) = \begin{cases} 1 & \text{if } t \geq 1 \\ t^\rho & \text{if } 0 < t < 1 \\ 0 & \text{otherwise} \end{cases}$$

where ρ is the power parameter and t is the information fraction.

For beta spending, rho was set to 1.0 which results in a spending function much like the Pocock method (i.e. equal spending between the interim and final analyses). For alpha spending, rho was set to 2.0 resulting a spending function somewhere between that found for the O'Brien-Fleming method and the Pocock method.

The planned interim analysis will be conducted after 75% of participants, of the re-estimate sample size, reach their 12-week visit and will also involve an analysis of the primary safety and efficacy endpoint, and a report of the frequency and severity of all related Adverse Events (anticipated and unanticipated). All endpoint analyses will be conducted simultaneously on the same data snapshot.

Minimizing Bias

The interim analysis will be designed to optimize usage of time and resources while controlling the Type I and II error rates and minimizing operational bias, in accordance with FDA's guidance on Adaptive Designs for Medical Devices.

Type I and II Error Rates

Statistical Analysis Plan		Page 22 of 23
Sponsor Luminopia	Study Luminopia One Amblyopia Vision Improvement Study	

Analyzing interim data during the study can lead to Type I error inflation and increase the chance of a false positive conclusion. The proposed group sequential design controls for Type I error inflation by using the well-established statistical method of alpha-spending, so the Type I error for the overall study is controlled at an acceptable level. A similar approach of a beta-spending function is used to keep the Type II error for the overall study at an acceptable level.

Operational Bias

The details of the group sequential design will be approved prior to collection of study data. To avoid any change in behavior between study personnel and participants before and after the interim analysis, the interim analysis will be conducted by the CRO and Sponsor without the involvement of participating investigators. The Medical Monitor will be informed of the interim analysis findings.

In the event that the study is stopped early for success or futility, randomization will be halted and the Medical Monitor will be asked to make a recommendation as to whether follow-up exams for existing participants should continue.

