3.4 Safety Reporting

3.4.1 Adverse Events

The participant and parent(s) will be asked about anticipated and unanticipated adverse events at each visit and phone call. The frequency of known and unknown adverse events will be summarized for all participants.

4 Study Design

The proposed study is a multi-center randomized, controlled, masked, clinical trial which compares mean change in amblyopic eye BCVA from baseline with Luminopia One (“therapeutic”), to refractive correction (“control”). One-hundred and forty participants ($n = 140$) aged 4-7 years (inclusive) will be enrolled. Participants will be randomized 1:1 to the “therapeutic group”, to use Luminopia One, or the “control group”, to undergo continued refractive correction, for 12 weeks of treatment.

A group sequential design with a single interim analysis will be used to allow stopping for either early success or futility in both primary safety and efficacy endpoints. The interim analysis will be conducted after 75% of participants have completed their 12-week follow-up visit. The overall Type I error rate was set at 0.05.

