6.6.1.3 Sensitivity Analysis

A sensitivity analysis will be conducted using multiple imputation for missing data and results of the analysis will be assessed for consistency with the primary analysis. Imputation will be based on regression methods using significant baseline covariates as independent predictors. Covariates will be determined based on a statistically or clinically significant association with the change in BCVA.

Missing data will be imputed using the PROC MI procedure in SAS. PROC MI imputes missing covariates in the order variables are listed on the VAR statement. The variables will be listed on the VAR statement in the order listed above.

Missing covariates will be imputed using Markov Chain Monte Carlo (MCMC) methods. For the endpoint, the method will be determined based on the pattern and nature of the missing data (e.g. FCS regression method for an arbitrary missing pattern). The imputation will be executed in two steps in SAS. The first step will use PROC MI to impute the missing covariates. For each imputed dataset generated in step 1, the endpoint status will be imputed in step 2 to create the final imputed datasets.

Explorations to omit predictors may be conducted if the multiple imputation models will not converge. For each multiple imputation model, 10 imputed datasets will be generated. The imputed datasets will then be combined for inference using standard methods such as those available in SAS PROC MIANALYZE or other valid statistical software.

If no significant predictors are identified, the following method for imputation will be used. Participants who completed the study will be categorized by age, sex, and treatment received. For a participant with missing data, the imputed value will be a random draw from those participants with data that have the same age, sex, and treatment.

Additional sensitivity analyses may be performed if deemed necessary.

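### The sponsor helps run the by-arm interim analysis while decisions that can reach the primary result are still open

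*SAP*

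**What the plan says.** Section 4 (Study Design) sets one look: "The interim analysis will be conducted after 75% of participants have completed their 12-week follow-up visit". Section 6.9.2 says the interim "will also involve an analysis of the primary safety and efficacy endpoint, and a report of the frequency and severity of all related Adverse Events". Both primary endpoints are differences between arms (6.6.1 and 6.6.2), so whoever runs the interim sees results by arm.

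Under Minimizing Bias, section 6.9.2 gives the aim as "controlling the Type I and II error rates and minimizing operational bias, in accordance with FDA's guidance on Adaptive Designs for Medical Devices". Under Operational Bias it says that "the interim analysis will be conducted by the CRO and Sponsor without the involvement of participating investigators", and then: "The Medical Monitor will be informed of the interim analysis findings". The section names no separate statistician, committee or firewall. It does not limit which sponsor or CRO staff see the results.

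Three provisions elsewhere can still be exercised after the look:
- Section 6.2 removes from the ITT set randomised participants later judged not to have met eligibility. It gives no deciding role and no deadline.
- Section 6.8 lets sites with fewer than 5 participants be merged for a site-by-treatment test at the 0.15 level. A significant result means the primary analysis must be adjusted for site.
- Section 7 requires an amended SAP for changes, with approval before the analysis only where that can be done. It also allows other departures prompted by the data or by missing values, to be explained in the study report.

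**The concern.** Keeping investigators out protects conduct at the sites. It does nothing about the party that can influence analysis sets, model adjustment and SAP amendments. If the trial continues, the sponsor holds the exact interim estimate and the by-arm safety tables while the three provisions above remain usable. A later ITT removal, site merger or amendment could then be influenced by the known comparison. Even if it were not, the sponsor could not show that from the document.

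This matters most when the result is borderline, and that is exactly when this design continues. Participants are not masked in this trial (4.2), so limiting who knows the comparative result is a worthwhile protection alongside the masked examiners.

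**Working it through.** **Inputs (SAP section 5).** One-sided alpha 0.05; beta 0.10; power-family spending with rho 2.0 for alpha and 1.0 for beta; information fraction t = 0.75; difference 0.075 logMAR; SD 0.140; 1:1 allocation; 132 evaluable, 140 enrolled.

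**Step 1: reproduce the plan's figures.**
- Alpha spent at the interim: 0.05 × 0.75² = 0.0281, so the success bound is Z = 1.909.
- Beta spent at the interim: 0.10 × 0.75 = 0.075.
- Solving both looks with binding futility gives drift θ = 3.066.
- n per arm = 2 × (0.140 × 3.066 / 0.075)² = 65.5, or 131.0 in total. Rounded up, this is 66 per arm and 132 in all, as stated.
- Futility bound: 3.066 × √0.75 − 1.440 = 1.216. P(Z < 1.216) under no effect = 0.888, against the stated 89%.

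With non-binding futility the total would be 138.6, so the stated 132 corresponds to a binding bound.

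**Step 2: bounds in logMAR.** Evaluable at the look: 0.75 × 132 = 99, or 49.5 per arm. SE = 0.140 × √(2/49.5) = 0.02814.
- Futility: 1.216 × 0.02814 = 0.034
- Success: 1.909 × 0.02814 = 0.054

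**Step 3: probability of continuing.** For a true benefit d, P(continue) = Φ(1.909 − d/SE) − Φ(1.216 − d/SE). At d = 0.075, d/SE = 2.665 and the result is Φ(−0.756) − Φ(−1.449) = 0.225 − 0.074 = 0.151.

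| True difference (logMAR) | d/SE | P(continue) |
|---|---|---|
| 0 | 0 | 0.084 |
| 0.0375 | 1.333 | 0.264 |
| 0.050 | 1.777 | 0.265 |
| 0.075 (design value) | 2.665 | 0.151 |
| 0.119 (pilot-based, section 5) | 4.229 | 0.009 |

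Using the unrounded 65.5 per arm, the entry at 0.075 becomes 0.153.

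**Step 4: data still to come.** 132 − 99 = 33 evaluable participants. On the enrolment count, 140 − 105 = 35.

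**Step 5: which open decisions reach the primary result.**

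| Decision | Section | Reaches the primary analysis? |
|---|---|---|
| Removal of ineligible participants from ITT | 6.2 | Yes, ITT is the primary set |
| Combining small sites, then site adjustment | 6.8 | Yes, it can change the primary model |
| SAP changes and other departures | 7 | Yes, potentially |
| Classification of major deviations | 6.2 | No, PP set, supportive |
| Imputation covariates and method | 6.6.1.3 | No, the primary analysis imputes nothing |
| Extra sensitivity analyses | 6.6.1.3 | No |

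**The case against.** The other side has a good deal to say, and much of it stands.

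- **Most of the primary analysis is fixed:** ITT, no imputation, in-window visits and a single treatment term. A reader might infer that every open choice threatens the primary result, pointing to "Additional sensitivity analyses may be performed if deemed necessary" or to the imputation covariates. The SAP does not support that, because those choices feed supportive analyses only.
- **Deviation classification.** A reader might infer that the rule "Protocol deviations will be reviewed and defined as major prior to analysis" of outcomes fails for the last quarter of participants. It does not strictly fail. The SAP does not say that the sponsor classifies deviations, and an aggregate interim difference does not disclose the outcomes of participants not yet analysed.
- **A firewall hides less than it seems.** The bounds are set in advance, so a bare decision to continue already places the interim difference between about 0.034 and 0.054 logMAR. The exact estimate adds only a position inside a window about 0.02 logMAR wide, or 0.2 line. The by-arm safety tables are a further real difference.
- **Other protections exist.** Acuity and stereoacuity are measured by masked examiners (4.2), and the group sequential details are approved before data collection (6.9.2).
- **Unseen text could help.** The protocol and the Masking Plan cited in 6.2 are not at hand, and the visible numbering runs from 6.9 to 6.9.2. Any of these might restrict access within the sponsor. Even so, 6.9.2 assigns the analysis to the sponsor, so its wording would still need to be reconciled with them.
- **Type I error.** A reader might infer that sponsor access breaks error control. Continuing past the futility bound and then using the planned final critical value (1.639) would raise one-sided error from 0.050 to 0.0585. Nothing in the SAP says the bound may be overruled, so this is not a finding.

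None of this closes the three decisions that do reach the primary result.

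**Conclusion.** The concern holds in a limited form, and the plan should be changed. Section 6.9.2 exposes the sponsor to by-arm results by an explicit rule, and the ITT-removal, site-combining and SAP-change provisions stay open afterwards. This falls short of the section's aim. It is not a flat contradiction of it, because keeping investigators out does serve part of that aim.

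The exposure arises only if the trial continues: about 8% at no effect, 26% to 27% at 0.0375 to 0.050 logMAR, 15% at 0.075 and 1% at 0.119. These figures assume SD 0.140, 132 evaluable participants, binding futility, a look at exactly 75% information, and a stopping decision driven by efficacy alone. Section 6.9.2 mentions a re-estimated sample size, and a different total would shift them. The size of any resulting bias cannot be derived from the SAP, and nothing in it suggests intended misuse. How far trial conduct could be affected depends on how many of the last quarter are already randomised at the look, and the SAP gives no accrual rate.

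**What to change.** Amend section 6.9.2 so that:
- the CRO already engaged conducts the interim behind a firewall;
- the sponsor and study team receive only one of three messages: stop for success, stop for futility, or continue;
- by-arm results are released only after a stop or the final database lock, except that the Medical Monitor may receive the safety tables.

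Before the interim data cut, lock the ITT-exclusion rule (with a named deciding role), the site-combining rule in 6.8, and the SAP itself.

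The cost is SAP wording and a separation of staff within the CRO. The SAP does not describe CRO staffing, so that separation needs confirming. The sample size stays at 132 evaluable and 140 enrolled. The sponsor gives up sight of by-arm data if the trial continues. The implied window noted above remains, because any pre-specified boundary reveals it.
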